7.1.1.3 Pharmacodynamic (PD) Measurements

See the Ivy Brain Tumor Center Laboratory Manual for details regarding collection, processing, packaging and shipment.

Identification of a positive PD effect (as defined by a significantly >30% decrease in the percentage of phospho-RB+ cells as well as phospho-S6+ cells) will be based upon comparative analysis of archival and post-treatment tumor tissue. Tumor tissues will be analyzed for pRB and total RB by immunohistochemistry (IHC). IHC analysis will be used to identify the status of pRB, RB, pFOXM1, FOXM1, pS6, S6, p-4EBP, cleaved caspase 3 and MIB-1 (ki67) in archival versus ribociclib+everolimus treated GBM tissue samples. For immunohistochemistry, the staining will be quantified using Aperio Brightfield Toolbox Software available at Barrow Neurological Institute. In addition, western blotting will be performed for pRB (S780), total RB, cleaved caspase 3 and MIB-1 on frozen treated tumor tissue and analyzed using the LiCOR Odyssey Imaging system. For comparison, treatment naïve tumor tissue with similar pathology from the Biobank will be used. The normalized average staining and/or luminescence for banked treatment naïve tumor will be used as a baseline to determine the pharmacodynamics of CDK4/CDK6 inhibition in the treated tumor tissues.

7.1.1.4 Biomarker Evaluation in Blood Samples

See the Ivy Brain Tumor Center Laboratory Manual for details regarding collection, processing, packaging and shipment. Pre-treatment blood sample will be collected for biomarker evaluation and baseline analysis. The tests include genetic sequencing to obtain status of the germline

mutations, liquid biopsy for tumor DNA or tumor secreted extra-cellular vesicles to identify biomarkers that will help predict drug efficacy.

7.1.1.5 Biomarker Evaluation in Tumor Samples

It has been shown that mTOR inhibition sometimes leads to paradoxical activation of upstream PI3K pathway activation. To assess this, protein from FFPE slides from pre- and post-treatment samples will be extracted and be analyzed by nanostring nCounter analysis system for their cancer panel examination. This cancer panel includes key components in the PI3K/mTOR signaling pathway, cell cycle pathway, MAPK as well as apoptosis pathways. The system also allows simultaneous comparison with protein and mRNA expression. This would allow comparison with surgical tissue with archival tissue.

Additional downstream target genes for E2F1 and mTOR pathways will be analyzed. Whole exome sequencing and RNAseq will be performed (Novogene). RNA and DNA will be extracted from matched archival and treated tissues (i.e.: pre- and post-treatment) for all patients, with blood samples as germline normal controls. RNA-sequencing and Exome sequencing will be performed to analyze differences in expression, mutations and copy number variations in genes before and after treatment. In addition, quantitative RT-PCR analysis will be performed for downstream genetic targets of E2F1 involved in cell cycle (CCNA1, CCNE1, CCNB1, CDK2, and CDK1), DNA replication (MCM2, MCM3, MCM5, MCM7, CDT1 and CDC6) and mitosis (CDC20, PLK1, MAD2 and CCNB1) to assess the effect of CDK4/6 inhibition. Since mTORC1 increases HIF1 α and phosphorylated STAT3 protein levels, we will also assess expression levels of HIF1 α and STAT3 target genes (VEGFa, MYC, CCND1 and BIRC5).

In addition, gliomas can be sub-classified by IHC as mesenchymal, proneural, or classical signatures based on the sequencing analysis and comparison to the TCGA database.

See the Ivy Brain Tumor Center Laboratory Manual for details regarding collection, processing, packaging and shipment.

7.1.1.6 Patient Derived Xenografts (PDX)

Participant-related tissue, cells and fluids from outpatient and inpatient sources will be collected by St. Joseph's Hospital and Medical Center (SJHMC); tissue will be processed, and stored by the IBTC team according to standard collection, processing, and storage procedures and with Institution Biosafety Committee (IBC) approval. The IBTC team will prepare all tissue samples according to approved protocols and/or standard procedures (also called Working Instructions, WIs) for storage, development into cell lines, creation of Patient-derived xenografts (PDXs) and/or preparation for histochemistry, as needed. Only SJHMC will be asked to collect tissue and provide to the IBTC. If a patient does not qualify for the treatment portion of the trial, the patient's intra-operative tissue may be collected if the patient has signed the informed consent and agrees to the tissue collection.

See the Ivy Brain Tumor Center Laboratory Manual for details regarding collection, processing, packaging and shipment.

7.1.1.7 Requirements for Historical and Post-treatment Tissue Samples

See the Ivy Brain Tumor Center Laboratory Manual for details regarding collection, processing, packaging and shipment.

7.1.1.7.1 Historical/Archival Tissue Samples

Pretreatment archival tissue samples will be requested to evaluate for PD and biomarkers to determine study eligibility after obtaining informed consent. Archival tissue will be requested from pathology lab.

Request will be for approximately 3-10-micron sections of archival tissue FFPE blocks which contain > 3 mm x 3 mm portions of viable tumor, on 10 unstained slides, a representative H & E slide from this tissue, and 12 scrolls of 20-micron thickness of the pathology core tissue for (2 scrolls per 2 ml tube), if there is adequate tissue available. Adjustments to the request may be made based on the available tissue. If adjustments are necessary, the decision should be made in conjunction with the nursing team, pathology lab and research lab.

7.1.1.7.2 Intraoperative Tissue Samples

Post-treatment surgical tissue should be placed in formalin until taken to hospital histology lab where it will be prepared as a FFPE block (see [Appendix 3](#) for tissue fixation protocol) and then made into approximately 3-10-micron sections of 20 unstained slides plus one H & E slide and 12 scrolls of 20-micron thickness of the pathology core tissue for (2 scrolls per 2 ml tube), if there is adequate tissue available. In addition, one tumor sample (dimensions, 0.5 cm³) will be collected from patients and divided into two equal portions.

The H&E slide will be examined by neuropathologist to confirm the presence of viable tumor in the resected tissue before proceeding with PD analysis.

7.1.1.8 Response Assessment in neuro-oncology criteria (RANO)

In Phase 0, RANO criteria will be used to confirm recurrence. In Phase 2, only those patients who have received at least one cycle of therapy and obtained an MRI in Phase 2 will be considered evaluable. Patients who have disease progression prior to the end of Cycle 1 will not be considered evaluable. The Phase 2 baseline MRI will be the first MRI taken post-operatively. Subsequent MRIs will be compared to the Phase 2 baseline.

MRI scans will be evaluated using the Criteria for response assessment incorporating MRI and clinical factors ([Chukwueke, 2018](#))

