Due to persistent negative PK effects from everolimus, despite no adverse events limiting drug dosing, additional dose-levels will employ a single, high-dose administration of everolimus. Other combination drug studies have suggested 70mg weekly as a maximal-tolerated dose. As a lead-in to this combination dose in our study, a new dose level at 50mg once prior to surgery (in combination with 600mg ribociclib) will be introduced. This lead-in dose will give rise to 60mg at the next level and 70mg at the final level. Similarly, the phase 2 component of the study will reflect this new dosing regimen for patients with PK and PD effects from both drugs. Specifically, a lead-in regimen at 50mg q weekly in Phase 2 (in combination with ribociclib) will then be escalated towards 70mg weekly.

3 Objectives and endpoints

	Objective	Endpoint
Primary	
• To determine the dose-limiting toxicity (DLT) and maximum tolerated dose (MTD) for study drug when administered in combination.• To identify recurrent high-grade glioma patients with positive PK and PD effects.	
• MTD: highest dose of drug that did not cause a DLT in > 17% of participants• PK: total and unbound ribociclib and everolimus concentrations in non-enhancing and contrast-enhancing tumor tissue samples• PD: pRB-positive cells and pS6-positive cells
Secondary	
• To explore safety and efficacy in recurrent high-grade glioma patients with demonstrated PK and PD effects and determine RP2D• To describe PK for Phase 2 patients	
• Progression-free survival (PFS)• Overall survival (OS)• Drug-related toxicity• RP2D• Systemic PK profiles of ribociclib and everolimus when combined.
Exploratory	
• To explore evidence for CDK4/6 and mTOR pathway activity in tumor tissue (as compared to	
• Quantification of total and phosphorylated forms of Rb, FoxM1, S6, 4EBP, as well as cleaved Caspase-3 and MIB1. Expression of Cyclin D1,

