Phase 0 participants who do not proceed to Phase 2 will be contacted every 3 months by letter or phone for collection of survival data for up to 5 years. The start of follow up for long-term survival begins following completion of the Day 30 safety follow up call.

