4.1.2 Phase 2 Dose expansion

Patients with tumors demonstrating favorable PK and PD will proceed to Phase 2 Dose Expansion. In Dose Levels 1-3, patients will continue treatment with the same treatment level as given in Phase 0, patients should take the treatment continuously in 28d cycles with 3 weeks on / 1 week off after surgery. In Dose Level 4+, patients should take everolimus in one dose weekly; ribociclib will be taken for 21 consecutive days followed by 1 rest week. The dose will be per Table 7. If more than one DLT is observed in 6 patients in the Phase 2 dose expansion, the enrollment will be stopped and the previous lower dose level will be considered the RP2D and will be given for the remaining patients enrolled. If more than one DLT is occurred with the Level 0, the study will be stopped due to toxicity. Typically DLTs are defined by 1 cycle of treatment, which is 28 days. Since Phase 0 treatment is given for only 5 days, Phase 0 dose escalation will only be determined by Phase 0 DLT rules unless determined otherwise by the DSMB. Patients will be treated until unacceptable toxicity is observed, or until disease progression as assessed by radiographic or clinical metrics. Preliminary rates of progression-free survival in patients with high-grade gliomas treated with ribociclib+everolimus will be measured through radiographic and clinical response metrics, specifically Response Assessment in Neuro-Oncology (RANO) criteria and investigator discretion. Phase 2 participants will return to the clinic to monitor safety per the schedule of events until treatment is ended and will then be contacted approximately every 3 months by letter or phone for collection of survival data. The start of follow up for long-term survival begins following completion of the Day 30 safety follow up call.. All Phase 0/2 participants will be followed for survival for up to 5 years.

Common Toxicity Criteria Adverse Event (CTC AE 4.03) will be utilized to review ribociclib+everolimus treatment effects in patients with brain tumors.

Trough steady-state blood samples will be obtained on days 1, 8, 15, and 22 of cycles 1 and 2 prior to the administration of ribociclib+everolimus on that day. Note: ribociclib+everolimus will be administered in the clinics on the clinic visit days to ensure the collection of trough level samples.

PHASE 2 STUDY				
	Cycle 1 (28 d)	Cycle 2 (28d)	Subsequent cycles (28d)	End of study
Day of cycle	D1, D8, D15, D22	D1, D8, D15, D22	N/A	N/A

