6.1.5 Guidelines for continuation of treatment beyond tumor resection (Optional Phase 2)

Patients with positive PK and PD responses will be provided the option of continuing on therapy until tumor progression. PK data evaluates the drug concentration in enhancing and non-enhancing region of the tumor. PD analysis evaluates the biomarker response after 5-day treatment and compares this with archival tissue. If both are positive the patients will be enrolled into Phase 2 portion of the trial with the same dose level taken during Phase 0 (unless there is more than one DLT observed in Phase 2, see Section 4.1.2). If the PD data is not conclusive due to treatment effect or limited tissue samples from the surgery, the PK data would be the primary guidance on deciding phase 2 enrollment.

Some anticipated risks and safety considerations of the ribociclib+everolimus combination will be closely monitored. Preclinical and Phase I clinical data available from ongoing studies with ribociclib and everolimus separately suggest few overlapping toxicities for the proposed

Initial Version date: 10/16/2018

Revision date: 03/11/2019, 5/07/2019, 09/26/2019, 03/17/2020, 08/26/2024

combinations. Special attention will be paid to blood counts (cytopenias), mucositis, liver function test abnormalities and QTc prolongation. Clinical data from the [CLEE011X2101] study do not show marked accumulation in ribociclib with time, suggesting that it does not substantially inhibit its own metabolism or clearance. Everolimus and ribociclib are *in vitro* inhibitors and substrates of CYP3A4, and the latter is also a time-dependent CYP3A4 inactivator. The available preclinical and clinical data therefore suggest the possibility of a drug interaction, specifically one that may increase exposure to everolimus. Based on simulation using Simcyp software (Simcyp Version 12, release 1), the projected increase in the AUC_{0-6h} of everolimus was 3.5-fold following the starting daily dose of 200 mg ribociclib co-administered with 2.5 mg of everolimus for 14 days. No significant effect on ribociclib metabolism was predicted when co-administered with everolimus. Appropriate eligibility criteria, dose modification guidelines and stopping rules are included in this protocol.

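### The Phase 2 evaluability rule drops patients who progress in Cycle 1 without saying whether it governs PFS; applied to PFS, it could only raise the curve

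*Combined protocol and SAP*

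**What the plan says.** Section 7.1.1.8 (RANO) holds the only evaluability rule for Phase 2. Its first part is that "only those patients who have received at least one cycle of therapy and obtained an MRI in Phase 2 will be considered evaluable". Its second part is that "Patients who have disease progression prior to the end of Cycle 1 will not be considered evaluable". Neither part names an endpoint. The section adds that "The Phase 2 baseline MRI will be the first MRI taken post-operatively".

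PFS is defined in a subsection of the same section, 7.1.1.8.3, as time from surgery to progression. The secondary endpoint table in section 9.6 measures it from surgery to recurrence. Section 9.7.1 measures it from surgery to progression or death from any cause, makes it a key secondary endpoint of the Phase 2 component, and plans Kaplan-Meier estimates with a 95% CI for the median. Section 4.1.2 says: "Preliminary rates of progression-free survival in patients with high-grade gliomas treated with ribociclib+everolimus will be measured through radiographic and clinical response metrics", and names RANO and investigator discretion as the means.

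On analysis sets, the text under 9.3.1 (Full Analysis Set) only says who is responsible for the analysis. Section 9.4 expects exclusions from that set to be summarised but gives no criteria. Section 9.6.1 says that there will be no separate SAP.

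**The concern.** A patient who progresses in Cycle 1 has one of the shortest PFS times in the study. A rule that removes such patients because they progressed selects on the outcome being estimated. The plan neither applies the rule to PFS nor excludes that reading, and it defines no other set. Two analysts could therefore report different PFS from the same data, and in an open-label study the choice could be made after the outcomes are known.

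The first part of the rule raises a lesser problem. It also removes patients who stop within a cycle for toxicity without progressing, and the effect of that on PFS has no fixed direction. The MRI condition matters only if the post-operative scan does not count as a Phase 2 MRI. Section 7.1.1.8 calls that scan the Phase 2 baseline, while Table 13, as extracted, places it in the Phase 0 follow-up column.

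The definitions are a second inconsistency: 7.1.1.8.3 and 9.6 do not name death as a PFS event, and 9.7.1 does.

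**Working it through.** **The plan's own figure.** Section 9.7.1 expects 3 to 12 patients in Phase 2. This reproduces: 50% × 6 = 3, and 50% × 24 (three time cohorts of 8) = 12. The total also reproduces: 24 / 0.8 = 30. The documents give no PFS median, rate or event count.

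**Inputs.** From the documents: cycle length 28 days and MRI at least every 3 months (section 7.1). Assumed: median PFS *m* = 2, 3, 4 or 6 months from Cycle 1 Day 1; a Weibull curve with shape *k* = 1.5 (rising hazard), 1 (constant) or 0.8 (falling); and a share *c* of Cycle 1 progressions recognised as such.

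**Formulas.**
- *d* = 28 / 30.44 = 0.92 months
- S(x) = exp(−(x/L)^k), with L = m / (ln 2)^(1/k)
- Share excluded: ex = c(1 − S(d))
- Curve kept, x < d: 1 − (1 − c)(1 − S(x)) / (1 − ex)
- Curve kept, x ≥ d: S(x) / (1 − ex)
- Shift = the time at which the kept curve equals 0.5, minus m

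A fixed interval from surgery to Cycle 1 adds the same amount to both medians and cancels.

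**Direction.** Before d, (1 − c)/(1 − ex) is at most 1 because ex ≤ c. After d, 1/(1 − ex) is at least 1. The kept curve is therefore never below the full curve, for any S.

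**One case in full.** Take m = 3, k = 1, c = 0.5. Then L = 3/0.693 = 4.328, S(0.92) = 0.8085 and ex = 0.5 × 0.1915 = 0.096. Solve S(x) = 0.5 × 0.904 = 0.452, which gives x = 4.328 × 0.794 = 3.44, a shift of +0.44 months.

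**All cases** (values for m = 2 / 3 / 4 / 6):

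| Hazard | Share recognised | Excluded, % | Shift in median, months |
|---|---|---|---|
| Rising | half | 9.7 / 5.6 / 3.7 / 2.0 | +0.19 / 0.16 / 0.14 / 0.12 |
| Rising | all | 19.4 / 11.1 / 7.4 / 4.1 | +0.40 / 0.33 / 0.29 / 0.24 |
| Constant | a quarter | 6.8 / 4.8 / 3.7 / 2.5 | +0.20 / 0.21 / 0.22 / 0.22 |
| Constant | half | 13.6 / 9.6 / 7.4 / 5.0 | +0.42 / 0.44 / 0.44 / 0.45 |
| Constant | all | 27.3 / 19.1 / 14.7 / 10.1 | +0.92 throughout |
| Falling | all | 31.1 / 23.6 / 19.3 / 14.3 | +1.42 / 1.52 / 1.60 / 1.72 |

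**Sampling error.** The asymptotic SE of the median with n patients is 1/(2√n f(m)). For this curve f(m) = k ln 2 / (2m), so SE = m / (k × ln 2 × √n). With n = 12 and k = 1 it is 0.83 / 1.25 / 1.67 / 2.50 months; divide by 1.5 or 0.8 for the other shapes. Only two entries exceed the matching SE, both at m = 2 with all progressions recognised: constant hazard (0.92 against 0.83) and falling hazard (1.42 against 0.83/0.8 = 1.04). The falling-hazard entry at m = 3 comes close (1.52 against 1.56).

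**Illustration without a model.** If 3 of 12 patients are progression-free at 6 months, the rate is 25%. Dropping 1, 2, 3 or 4 early progressors makes it 3/11 = 27%, 3/10 = 30%, 3/9 = 33% or 3/8 = 38%.

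**The case against.** The strongest reply is that the rule concerns response, not PFS. It sits under response assessment, and section 9.7.1 defines PFS and its Kaplan-Meier analysis with no evaluability condition. Response also has its own uses in the protocol: Table 13 schedules a RANO response assessment, section 7.1.1.2 plans to relate metabolite changes to clinical response, and 7.1.1.8.1 and 7.1.1.8.2 define the response categories. This stands as a reason why the rule may never touch PFS. It does not settle the matter, because the rule names no endpoint and PFS is defined within the same section.

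A reader might infer that the plan does exclude early progressors from PFS. The documents do not say so. A reader might also infer that the PFS population is wide open, since the objective speaks of patients with demonstrated PK and PD effects and section 6.1.5 says that, where PD is inconclusive, "the PK data would be the primary guidance on deciding phase 2 enrollment". That goes too far. Sections 4.1.2 and 9.7.1 tie PFS to treated Phase 2 patients, and those who do not enter Phase 2 are followed only for survival. The real gap is whether the rule filters Phase 2 patients.

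On size, every PFS input is assumed, and with MRI required only every 3 months, recognition of all Cycle 1 progressions is unlikely. This stands, and it weakens the larger figures most.

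On death, the RANO progression category in 7.1.1.8.1 includes failure to return for evaluation because of death. This narrows the gap between the definitions but does not make them the same. Nor does that category contradict the evaluability rule: one classifies progression, the other filters patients.

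**Conclusion.** The concern holds in conditional form. The evaluability rule does not state its scope, no analysis set resolves it, and if it is applied to PFS the Cycle 1 exclusion can move the curve only upward or not at all. The direction needs no assumption about the PFS distribution.

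The size cannot be fixed from the documents. On assumed medians of 2 to 6 months from Cycle 1 Day 1, it is about +0.1 to +0.4 months under a rising hazard, +0.2 to +0.9 under a constant hazard, and up to about +1.7 under a falling hazard with every Cycle 1 progression recognised. None of these is a bound or an expected value. It would be wrong to conclude that reported PFS will be inflated by a month or more: that needs both the application to PFS and near-complete recognition in Cycle 1. Most of the shifts are below the sampling error with 12 patients, although they are systematic and would not average out.

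The conflict over death in the PFS definitions stands on the text alone.

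Severity is minor. PFS is exploratory and descriptive in 3 to 12 patients, there is no interim analysis (section 4.2), and no decision rule uses PFS. MTD, RP2D and the PK/PD endpoints are not affected.

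**What to change.** - In section 9.3, state that PFS is analysed in all patients who receive at least one Phase 2 dose. Count progression (radiographic or clinical) or death from any cause as an event, including in Cycle 1 and without a Phase 2 MRI.
- Keep patients who stop early without progression in the set, censored at their last disease assessment. The date must be stated because after treatment ends patients "will then be contacted approximately every 3 months by letter or phone for collection of survival data". Say also how a death found later in that follow-up is handled.
- In section 7.1.1.8, limit the evaluability rule to descriptive best response, and list early progressors there as progressive disease, in line with 7.1.1.8.1.
- Align the PFS definitions in 7.1.1.8.3 and 9.6 with the one in 9.7.1, which includes death.

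The cost is a short protocol amendment with sponsor and IRB review (section 11.1). It uses data already planned, with no new visits or scans. The downside is that reported PFS may be slightly less favourable than under the restricted reading.

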7.1.1.8.1 Phase 2 Evaluation of Target Lesions

Complete Response (CR)

Requires all of the following: complete disappearance of all enhancing measurable and nonmeasurable disease sustained for at least 4 weeks; no new lesions; stable or improved nonenhancing (T2/FLAIR) lesions; patients must be off corticosteroids (or on physiologic replacement doses only); and stable or improved clinically. Note: Patients with nonmeasurable disease only cannot have achieved CR; the best response possible is SD.

Partial Response (PR)

Requires all of the following: $\geq 50\%$ decrease compared with baseline in the sum of products of perpendicular diameters of all measurable enhancing lesions sustained for at least 4 weeks; no progression of nonmeasurable disease; no new lesions; stable or improved nonenhancing (T2/FLAIR) lesions on same or lower dose of corticosteroids compared with baseline scan; the corticosteroid dose at the time of scan evaluation.

Stable Disease (SD)

Requires all of the following: Does not qualify for CR, PR or progression; stable nonenhancing (T2/FLAIR) lesions on the same or lower dose of corticosteroids compared with baseline scan. In the event that the corticosteroid dose was increased for new symptoms and signs without confirmation of disease progression on neuroimaging, and subsequent follow-up imaging shows that this increase in corticosteroids was required because of disease progression, the last scan considered to show SD will be the scan obtained when the corticosteroid dose was equivalent to the baseline dose.

Progressive Disease (PD)

Defined by any of the following: $\geq 25\%$ increase in the sum of the products of perpendicular diameters of enhancing lesions compared with the smallest tumor measurement obtained either at baseline (if no decrease) or best response on stable or increasing doses of corticosteroids[†]; significant increase in T2/FLAIR nonenhancing lesion on stable or increasing doses of corticosteroids compared with baseline scan or best response after initiation of therapy[†] not caused by comorbid events (e.g., radiation therapy, demyelination, ischemic injury, infection, seizures, postoperative changes or other treatment effects); any new lesion; clear clinical deterioration not attributable to other causes apart from the tumor (e.g., seizures, medication adverse effects, complications of therapy, cerebrovascular events, infection, etc.) or changes in corticosteroid dose; failure to return for evaluation as a result of death or deteriorating condition; or clear progression of nonmeasurable disease.

